8.3. Trial Procedures

Muscle biopsies; performed by trained member of the study team. If participants regularly take aspirin they will be asked to stop this 3 days prior to each biopsy and restart the day after the biopsy.

Venepuncture; performed by trained research nurse.

1-RM leg extension strength test; established procedure; incremental increases in load until only one repetition can be completed

Physical activity (ActivPAL accelerometry); assessors will be trained.

Serum inflammatory markers will be measured using the Luminex system, and assessors will be trained.

8.3.1.Sub studies

None proposed

9. Adverse Event Reporting

9.1. Reporting Requirements

Non-CTIMPs

The collection and reporting of Adverse Events (AEs) will be in accordance with the Research Governance Framework for Health and Social Care and the requirements of the National Research Ethics Service (NRES). Definitions of different types of AEs are listed in the table of abbreviations and definitions. The Investigator should assess the seriousness and causality (relatedness) of all AEs experienced by the trial participant (this will be documented in the source data) with reference to the protocol.

9.2. Adverse Events

AEs are commonly encountered in participants aged 65 y and over.

D₂O has been known to cause vertigo and nausea although this is very unusual.

Trial name:	The effects of protein distribution and resistance exercise training on the muscle of older adults				
Protocol version number:	6.0	version date:	10-Apr-17	Page:	19 of 31

Any AEs as a consequence of the exercise programme over and above the expected and common muscle stiffness which occurs after the initial exercise sessions in those unaccustomed to regular exercise will be recorded.

The study team will use the UHB NHS Foundation Trust reporting system embedded within their governance structure.

9.3. Serious Adverse Events

Investigators will report AEs that meet the definition of an SAE In this trial, an SAE must fulfil at least one of the following criteria:

- Is fatal
- Is life-threatening
- Requires in-patient hospitalisation or prolongation of existing hospitalisation
- Results in persistent or significant disability/ incapacity
 - 9.3.1. Events that do not require expedited (immediate) reporting

N/A

9.3.2. Events that do not require reporting on a Serious Adverse Event Form

N/A

9.3.3. Monitoring pregnancies for potential Serious Adverse Events

N/A

9.4. Reporting period

Details of all AEs will be documented and reported from the date of informed consent, as participants will undergo an exercise familiarisation session prior the commencement of the protocol defined treatment (protein distribution diets) until the final day of administration of the treatment.

9.5. Reporting Procedure – At Site

9.5.1. Adverse Events

Information on AEs will be collected on an AE Form (and where applicable on an SAE Form). An AE Form will be completed and returned to the study team medical expert (and copied to the CI). The study team medical expert will be included in all AE/ SAE reporting processes.

9.5.2. Serious Adverse Events

AEs defined as serious and which require reporting as an SAE should be reported on an SAE Form. When completing the form, the Investigator will be asked to define the causality and the severity of the AE.

On becoming aware that a participant has experienced an SAE, the Investigator (or delegate) will complete, date and sign an SAE (DATIX) form. The form will automatically be sent (scanned and emailed – not faxed which is no longer considered best practice) to the Clinical Research Facility's Clinical Manager for review as soon as possible and no later than 24h after first becoming aware of the event. All SAEs will be reviewed formally every 2

Trial name:	The effects of protein distribution and resistance exercise training on the muscle of older adults				
Protocol version number:	6.0	version date:	10-Apr-17	Page:	20 of 31

weeks during Clinical Research Facility operations meetings which include representation from the Trust R&D office.

The SAE reference number will be quoted on all correspondence and follow-up reports regarding the SAE and filed with the actual SAE in the site file.

For SAE forms completed by someone other than the Investigator, the Investigator (or delegate) will countersign the original SAE to confirm agreement with the causality and severity assessments. The form will be returned to the Clinical Research Facility Manager and the copy kept in the site file.

The Investigators will report SAEs to their own Trust via the Clinical Research Facility in accordance with local practice using an electronic reporting system.

9.5.3. Provision of follow-up information

Participants should be followed up until resolution or stabilisation of the event. Follow-up information should ideally be provided on a new SAE Form.

9.6. Reporting Procedure – Trials Office

This is a low-risk study of exercise plus a dietary supplement versus exercise plus placebo. The Trials Office will not be involved. However we will report AEs and SAEs according to the UHB NHS Foundation Trust's electronic reporting system

Http://doha/datix/live/index.php?form id=20&module=INC

The PI will monitor any forms completed and reported through the CRF Clinical Manager / CRF operations meetings for trends. Additional input will be provided by University of Birmingham Clinical Research Compliance Team.

9.7. Reporting to the Competent Authority and Research Ethics Committee

9.7.1. Suspected Unexpected Serious Adverse Reactions

N/A

9.7.2. Serious Adverse Reactions

N/A

9.7.3. Unexpected and Related Serious Adverse Events

All events categorised as Unexpected and Related SAEs will be reported to the REC and the University of Birmingham (Sponsor) research governance team ([contact]) within 15 days.

9.7.4. Adverse Events

N/A

9.7.5. Other safety issues identified during the course of the trial

The REC will be notified immediately if a significant safety issue is identified during the course of the trial.

Trial name:	The effects of protein distribution and resistance exercise training on the muscle of older adults				
Protocol version number:	6.0	version date:	10-Apr-17	Page:	21 of 31

9.8. Investigators

Details of all Unexpected and Related SAEs and any other safety issue which arises during the course of the trial will be reported to Principal Investigators. A copy of any such correspondence should be filed in the Site File.

9.9. Data Monitoring Committee

The study team considers this to be a low risk study and as such have taken the decision to not commission a Data Monitoring Committee for this study.

9.10. Reporting to third parties

N/A

10. Data Handling and Record Keeping

10.1. Source Data

In order to allow for the accurate reconstruction of the trial and clinical management of the subject, source data will be accessible and maintained. Some data may be entered directly onto the CRF these are clearly identified and detailed below.

Type of Data	Source Document
Informed consent	Signed Informed Consent Form
Relevant Medical History and Current Medical Conditions	Health Questionnaire
Demographics	CRF
MMSE	CRF
Vital signs including blood pressure, heart rate, height and weight	CRF
1-RM leg extension strength	CRF
Physical activity measurement (ActivPAL) times and results	Printed report
Food diary	Printed report
Compliance questionnaire	Printed report
Adverse events	AE form
Trial Termination details	CRF

Trial name:	The effects of protein distribution and resistance exercise training on the muscle of older adults				
Protocol version number:	6.0	version date:	10-Apr-17	Page:	22 of 31

Diet plan/ exercise compliance	CRF

10.2. CRF Completion

Data reported on each Case Report Form will be consistent with the source data and any discrepancies will be explained. All missing and ambiguous data will be queried. Staff delegated to complete CRFs will be trained to adhere to UHB NHS Foundation Trust governance guidelines

In all cases it remains the responsibility of the site's Principal Investigator to ensure that the CRF has been completed correctly and that the data are accurate. Where applicable for the trial this will be evidenced by the signature of the site's Principal Investigator on the CRF.

The completed originals will be kept by the CI and a copy filed in the Investigator Site File.

10.3. Data Management

Individual data sets will be checked by the CI at regular intervals and any discrepancies highlighted and listed. These will be viewed and discussed by the supervisory team.

10.4. Archiving

Data will be archived according to UHB NHS Foundation Trust governance guidelines.

11. Quality control and quality assurance

11.1. Site Set-up and Initiation

This is a low risk single-centre study which the study team do not consider is reliant upon Trials Office support. An Investigator Site File will be maintained and which will include essential documentation, instructions, and other documentation required for the conduct of the trial.

11.2. Monitoring

11.2.1. On-site Monitoring

The study team will allow Trials Office staff to monitor the study, including access to source documents as requested.

11.2.2. Central Monitoring

This is a small single-site study and the study team considers that central monitoring is not applicable.

11.3. Audit and Inspection

The investigator will permit trial-related monitoring, quality checks, audits, ethical reviews, and regulatory inspection(s) at their site, providing direct access to source data/documents. The investigator will comply with these visits and any required follow up.

11.4. Notification of Serious Breaches

In accordance with the Research Governance Framework for Health and Social Care 2005, the sponsor of the trial is responsible for notifying the REC and R&D departments of any

Trial name:	The effects of protein distribution and resistance exercise training on the muscle of older adults				
Protocol version number:	6.0	version date:	10-Apr-17	Page:	23 of 31

serious breach of the conditions and principles of GCP in connection with that trial or the protocol relating to that trial.

Any serious breaches will also be reported to the University of Birmingham's (the Sponsor's) research governance team ([contact])

Further recruitment to the study may be suspended in the event of serious and persistent non-compliance with the protocol and/or GCP, and/or poor recruitment. Any major problems identified during monitoring may be reported to the Trial Management Group and the REC.

12. End of Trial Definition

The end of trial will be 12 months after the last data capture. The Trials Office will notify the REC the trial has ended and a summary of the clinical trial report will be provided within 12 months of the end of trial.

13. Statistical Considerations

13.1. Definition of Outcome Measures

13.1.1. Primary outcome measures

See section 2.2.

13.1.2. Secondary outcome measures/exploratory endpoints

See section 2.2.

13.2. Analysis of Outcome Measures

All data will be entered into a database. Using SPSS Statistics for Windows, Version 21.0. Armonk, NY: IBM Corp., data analysis will be conducted by the PhD student on both an intention to treat and per protocol basis (i.e. values for all measurements, completed at least 75% of exercise sessions, and complied with the study diet). Comparisons are planned between Pulse and Spread distribution groups for change in all outcome measures. In the case of MPS, a comparison between trained and untrained legs is also planned. All data will be checked for normality and appropriate log transformations applied prior to *t*-tests for primary and secondary outcome measures.

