2.2. Outcome Measures

All outcome measures will be made by members of the study team (i.e., research nurses, the PhD student).

The primary outcome measure will be muscle protein synthesis

Secondary outcomes are:

- Serum inflammatory markers (IL-1, IL-6, IL-8, TNF-alpha, and the anti-inflammatory cytokine IL-10)
- Leg extension strength in each leg
- Food diaries
- Feasibility of the trial, including participants' willingness to be randomised, number of eligible participants, number of participants recruited, compliance with the study diets, adherence to exercise and the time taken to collect data

Muscle biopsies will be taken from the thigh at baseline and 2 weeks to measure muscle protein synthesis; at baseline a sample from one thigh will be taken, and at 2 weeks a sample from each leg will be taken, for comparison between exercised and non-exercised legs (see intervention). Saliva samples will also be taken at these times, and an additional saliva sample after 1 week, to allow calculation of MPS. Serum inflammatory markers and 1-RM leg extension strength will be measured at baseline and 2 weeks, and the analysis metric will be change from baseline. Physical activity level will be measured before the start of the study to characterise the population. 3-day food diaries will be completed at baseline and in the final days of the intervention to determine compliance to the diet plan, and participants will be asked to complete a daily questionnaire to confirm whether they have eaten one of the study meals for each meal of the day (yes/no answers). All assessments will take place in the Wellcome Trust Clinical Research Facility.

Trial name:	The effects of protein distribution and resistance exercise training on the muscle of older adults					
Protocol version number:	6.0	version date:	10-Apr-17	Page:	12 of 31	

3. Trial Design and Setting

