6.3. Blinding

Due to the nature of the intervention, blinding will not be used. The intervention is protein distribution, and as this is to be achieved by dietary manipulation, participants will be aware of which protein distribution they are receiving.

7. Trial treatment / intervention

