7.5. Accountability Procedures

Compliance with RET will be assessed by recording attendance to each session. Adherence to diet plans will be monitored using a 3-day food diary completed in the final days of the intervention, and a daily questionnaire in which participants will be asked to state whether or not they have consumed a meal from the diet plan for each daily meal.

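### Section 6.3 drops blinding for everyone for a reason that covers participants only, and the literal per-protocol rule can exclude valid MPS data from the per-protocol analysis

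*Protocol*

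**What the plan says.** Section 6.3 states: "Due to the nature of the intervention, blinding will not be used". The only explanation is that the intervention is dietary, so "participants will be aware of which protein distribution they are receiving". No role is exempted.

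Section 2.2 names the primary outcome ("The primary outcome measure will be muscle protein synthesis") and says who measures: "All outcome measures will be made by members of the study team (i.e., research nurses, the PhD student". On the cytokine assay, section 8.3 says "Serum inflammatory markers will be measured using the Luminex system, and assessors will be trained"; it does not mention masking to allocation.

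Section 13.2 assigns the analysis and its sets as follows: "data analysis will be conducted by the PhD student on both an intention to treat and per protocol basis". It then lists three conditions for per-protocol membership: "values for all measurements, completed at least 75% of exercise sessions, and complied with the study diet". Section 7.5 describes the diet-compliance data: a food diary over three days near the end, and a form filled in every day, for which it says: "participants will be asked to state whether or not they have consumed a meal from the diet plan for each daily meal".

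**The concern.** The sentence in 6.3 is broader than its justification. A participant cannot be masked to the meals she eats, but a tube of serum or saliva or a biopsy can be processed without anyone knowing the diet, and a data set can be analysed with arms under neutral codes. As written, the protocol gives up protection that is available at little cost, and one person may both measure and analyse with the allocation in view. Section 2.1 states a directional expectation in favour of Pulse, which is the setting in which masking is most useful.

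The per-protocol definition raises a second point. Asking for every measurement, whatever outcome is being analysed, ties the MPS analysis to the completeness of unrelated items such as a cytokine or a food diary. With 10-12 participants per group, each avoidable exclusion matters.

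The trial is exploratory, so no confirmatory claim is at risk. However, section 13.2.5 intends the data to inform sample sizes for future studies. An MPS estimate affected by unmasked handling, or by a late choice of analysis set, would carry into that planning.

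**Working it through.** **1. Does the reason in 6.3 reach each role?**

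- Participants: yes. They follow the diet plan.
- Staff giving the diet plan and the one-to-one exercise sessions (7.3): not named, but masking is impractical because they deal directly with participants who know their diet.
- 1-RM tester: not named. Masking would need a separate assessor and would be fragile.
- Biopsy, saliva and serum assays: no. Nothing in the reason requires the laboratory to know the arm.
- Statistical analysis: no. Neutral arm codes suffice for a two-group comparison.

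The last two fall under the rule only because the statement in 6.3 is unqualified.

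**2. What does the all-measurements requirement do?**

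Take a participant with usable baseline and day-14 biopsies and saliva, full exercise attendance and good diet compliance, but one missing cytokine.

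- ITT analysis of MPS: included.
- Per-protocol analysis of MPS, read literally: excluded.
- Per-protocol analysis of MPS under an outcome-specific rule: included.

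The exercise criterion, by contrast, is objective. Section 8.2 schedules six sessions (visits 1 to 6), and 0.75 × 6 = 4.5, so at least 5 must be completed.

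**3. What would a free choice between the two sets cost?**

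The protocol gives no alpha, power, effect size or SD, so it has no figure to reproduce; its sample size of 20-24 is simply 2 × 10-12. The size was therefore estimated by simulation under no diet effect.

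Inputs and assumptions:
- 10 or 12 per arm (protocol).
- Two-sided alpha 0.05 (assumed).
- Independent normal outcomes and a pooled two-sample t-test (assumed; 13.2 plans t-tests).
- Per-protocol set a random subset of ITT, with the numbers kept as shown (assumed).
- 200,000 simulated trials per row.

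Quantity: P(p_ITT < 0.05 or p_PP < 0.05) = P(ITT) + P(PP) − P(both).

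| n per arm | kept per arm in per protocol | chance that either is below 0.05 |
|---|---|---|
| 10 | 9 | 0.065 |
| 10 | 8 | 0.072 |
| 10 | 7 | 0.077 |
| 10 | 6 | 0.082 |
| 12 | 11 | 0.064 |
| 12 | 10 | 0.071 |
| 12 | 8 | 0.078 |
| 12 | 7 | 0.082 |

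Each set alone gave 0.050-0.051. For n = 10 with 8 kept: 0.04995 + 0.05015 − P(both) = 0.07171, so P(both) = 0.0284. The two tests overlap heavily, which is why the result stays below the value for two independent tests, 1 − 0.95² = 0.0975.

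With one set named as primary and its membership fixed in advance, the chance returns to 0.05. The simulation says nothing about bias from unmasked assays or analysis. The protocol gives no basis for a figure there.

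**The case against.** **Much of this belongs in a statistical analysis plan.** Ranking ITT against per protocol, a numeric diet cut-off and locking the per-protocol list are commonly left to that document, which is not at hand. Section 13.2 commits to both analyses; it does not permit choosing one. This stands: the lack of a ranking or cut-off is not itself a fault of the protocol, and the 6.4-8.2% is conditional on a choice being made. What remains is text that the protocol itself fixes: the unqualified no-blinding statement and the all-measurements requirement. An analysis plan that masked the analyst would conflict with 6.3 as written.

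**Stronger readings that a reader might infer.**

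- *That the unblinded student decides per-protocol membership knowing the results.* No section says who decides or when. Simulated outcome-aware classification gives 10.1-10.7% with two borderline participants per arm and 14.2-15.9% with three, but that conduct is not described in the protocol.
- *That the per-protocol set is subjective.* Only diet compliance lacks a threshold; the other two criteria are objective.
- *That diet compliance differs between arms.* This is possible, but nothing in the protocol documents it.
- *That valid primary data are lost to the trial.* They are not, because ITT retains them. The all-measurements requirement is also a short parenthesis that could be read less literally.
- *That about three in ten false positives or exclusions are at stake.* Counting both legs and both sets gives 12-14%, and adding the trained-versus-untrained contrast 19-20%. Two legs in ITT alone already give 8.3-9.4%, and the leg contrast tests exercise, not diet; the proposed change removes neither. Likewise, six required measurements, each 95% complete and independent, would leave 0.95⁶ = 0.735 (74%) eligible. Both inputs are assumptions, and with fully clustered missingness 95% would qualify. Most day-14 measurements come from one visit, so clustering is likely.

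**Masking will be weak.** Section 5 allows the student to take consent, section 2.2 has the student measure outcomes, and there are only 20-24 participants. The week-2 diary may reveal the meal pattern. This stands as a limit on the benefit. Laboratory coding and analysis under neutral arm labels still help.

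**Conclusion.** The point holds in a limited form. Section 6.3 abandons blinding without qualification for a reason that applies to participants, leaving the assays and the analysis unmasked without justification, while one person is listed as both outcome assessor and analyst. Section 13.2, read literally, lets a missing unrelated measurement exclude a participant from the per-protocol MPS analysis, though not from ITT.

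The quantified part is modest: about 6.4-8.2% instead of 5% for one endpoint, if either set could be emphasised after results are known, with alpha 0.05 assumed and exclusions at random. The documents do not show that such a choice is intended, nor who assigns membership. For an exploratory trial without a success rule, the consequence is an avoidable risk of bias in the estimates passed to later studies, not a failed test. The change is worth making because it is specific and cheap.

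**What to change.** **Section 6.3.** Limit the no-blinding statement to participants, staff delivering the intervention and the 1-RM tester. Add that biopsy, saliva and serum samples carry only trial ID and time point, plus a neutral leg code for the two day-14 biopsies, so that assays and data reduction are done without knowledge of arm. Add that the analysis is run on arms coded A and B, with the code held by the hospital statistician who already prepares the randomisation (6.2), until the data and the per-protocol list are locked.

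**Section 13.2.** Make the data requirement outcome-specific: a participant enters the per-protocol analysis of an outcome if the values for that outcome are available and the exercise and diet criteria are met. Fix membership before outcome data are seen, including a stated diet-compliance rule built on the daily questionnaire and the week-2 diary. The team should choose and justify the threshold, since the protocol gives no basis for a particular value. State ITT as primary and per protocol as supportive. The diet rule and the ranking may sit in the analysis plan if 13.2 refers to it.

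**Cost.** A few sentences, coded labels and one allocation file; no extra visits, participants or assessors. Masking of a student who has met the participants will be only partial, and 1-RM strength stays unblinded. The report should state both limits.

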- Lower limb fracture sustained within the previous 2 years; upper limb fracture within the previous 6 months; non arthroscopic lower limb joint surgery within the previous 2 years
- Any reason for loss of mobility for greater than 1 week in the previous 2 months or greater than 2 weeks in the previous 6 months
- Resting systolic pressure >200 mmHg or resting diastolic pressure >100mmHg
- Poorly controlled atrial fibrillation
- Poor (chronic) pain control
- Moderate/ severe cognitive impairment (MMSE <23)
- Renal impairment (Stage 4 or 5)

Intervention

Participants will be randomised to RET (x3 per week) + Pulse protein distribution or RET + Spread distribution.

Protein distribution: Daily protein intake will either be consumed in a Pulse distribution (meals of 10%, 80% and 10% of daily intake) or a Spread distribution (3 x 33%). This will be achieved using a diet plan which, if followed, will give these distributions, and will provide 1.2 grams of protein per kilogram of body weight per day. There will be a level of flexibility in the diets to allow for dietary requirements and personal preferences, and preliminary data indicate that protein supplementation may be required for some individuals in order to reach a protein intake of 1.2 g.kg⁻¹.day⁻¹. A commercial protein supplement will be used for this.

Resistance exercise training: Throughout the trial participants will complete 3 RET sessions per week of a unilateral leg extension model (6 x 8 repetitions at 75% 1-repetition maximum). The use of a unilateral model will allow comparison between exercised non-exercised legs, as well as between treatment groups.

Trial name:	The effects of prot	ein distribution and	d resistance exercise training o	on the muscle o	of older adults
Protocol version number:	6.0	version date:	10-Apr-17	Page:	5 of 31

Trial Schema

Telephone screening: health questionnaire

Pre-trial visit: Consent, health questionnaire, vitals (height, weight, blood pressure, heart rate), MMSE, unilateral RET familiarisation, food diary instructions, activity monitor attachment

Day 0: Blood sample, saliva samples (x2), muscle biopsy, D₂O administration, diet plan administration, unilateral RET session

Weeks 1-2: Unilateral RET session (3 per week)
Day 7: D₂O dose and saliva samples (x2)
Week 2: food diary

Day 14: 1-RM measurement, blood and saliva samples, muscle biopsies (x2)

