1.2.2. Justification for design

This standalone study is designed to measured acute effects of protein distribution in combination with resistance exercise. The study includes a unilateral RET component to allow measurement of effects with and without exercise. Protein distributions will be implemented through dietary manipulation to investigate whether this is feasible as a lifestyle intervention.

1.2.3.Choice of treatment

There is evidence to suggest that the distribution of protein intake may have an effect on muscle health in older adults, however this evidence is limited to two studies. Chronic resistance exercise training has been shown to be effective in improving muscle health, however no study has combined this with different protein distributions in older adults.

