2.1. Aims and Objectives

We hypothesise that there will be a significant difference in muscle health with different protein distributions. Based on previous studies, we hypothesise that improvements will be seen in both groups, however there will be greater improvement in the Pulse group.

Principal objective: Investigate the effect of dietary protein distribution on muscle protein synthesis (MPS) over two weeks, with and without RET, in the thigh muscle of older adults Secondary objectives:

- (i) Investigate whether protein distribution influences serum inflammatory markers
- (ii) Consider the feasibility of such an intervention in this population
- (iii) Determine whether the effects of RET on muscle strength is influenced by protein distribution
- (iv) Investigate whether changes in responsiveness of MPS predict changes in muscle strength

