8.2. Schedule of Assessments

-Screening (telephone call): Screening health questionnaire

Trial name:	The effects of protein distribution and resistance exercise training on the muscle of older adults				
Protocol version number:	6.0	version date:	10-Apr-17	Page:	18 of 31

- -Pre-trial visit (visit 0): Consent, health questionnaire, blood pressure measurement, MMSE, vitals measurement (height, weight, heart rate), unilateral knee extension exercise familiarisation (including 1-RM tests), food diary introduced, physical activity monitor attached for 7 days
- -Visit 1 (day 0): Muscle biopsy, blood sample, saliva samples, D₂O administration, unilateral RET session
- -Visit 2-6 (weeks 1-2): Unilateral RET session
- -Visit 7 (day 14): Blood and saliva samples, muscle biopsy (x2), leg extension 1-RM At-home activities:
- -Day 0: Saliva sample
- -Day 7: D₂O administration and saliva samples (x2) (or in CRF if scheduled for training visit)
- -Weeks 1-2: Daily compliance questionnaire
- -Week 2: 3-day food diary

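### Objective (iii) asks whether diet modifies the RET effect on strength, but Section 13.2 plans no comparison of the trained-minus-untrained leg difference between diets

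*Protocol*

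**What the plan says.** The relevant text is in five places in the protocol.

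- **Objective.** Section 2.1, secondary objective (iii): "Determine whether the effects of RET on muscle strength is influenced by protein distribution". The principal objective in the same section is "Investigate the effect of dietary protein distribution on muscle protein synthesis (MPS) over two weeks, with and without RET, in the thigh muscle".
- **Design.** Section 1.2.2: "The study includes a unilateral RET component to allow measurement of effects with and without exercise". The Intervention part of the Trial Summary adds: "The use of a unilateral model will allow comparison between exercised non-exercised legs, as well as between treatment groups".
- **Outcome.** Section 2.2 lists "Leg extension strength in each leg" among the secondary outcomes and sets the metric: "Serum inflammatory markers and 1-RM leg extension strength will be measured at baseline and 2 weeks, and the analysis metric will be change from baseline".
- **Analysis.** Section 13.2 compares Pulse with Spread on the change in every outcome, and then says: "In the case of MPS, a comparison between trained and untrained legs is also planned". The only test named is the t-test, after a normality check and log transformation where appropriate.
- **Other analyses.** Section 13.2.2 proposes no subgroup analyses, and no other section adds a contrast involving the legs.

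**The concern.** Objective (iii) asks whether one factor changes the effect of another. Diet varies between participants and RET varies between the legs of one participant. The quantity of interest is therefore the difference between diets in the within-person leg difference. The design provides for this, since both legs are tested for strength. Section 13.2 does not use it: it confines the leg comparison to MPS, and even for MPS it does not compare the leg difference between diets.

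At stake is what can be concluded about objective (iii). If Pulse shows a larger trained-leg gain than Spread, the planned test cannot say whether Pulse enhanced the response to training or raised strength in both legs regardless of training. The data that would separate the two are collected but have no stated role.

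**Working it through.** **1. What each contrast estimates.** For diet *d*, let *a_d* be the mean strength change common to both legs and *r_d* the additional change due to RET. The expected change is *a_d + r_d* in the trained leg and *a_d* in the untrained leg.

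| Contrast | Estimates | Planned in Section 13.2? |
|---|---|---|
| Pulse − Spread, trained leg | (a_P − a_S) + (r_P − r_S) | Yes, as change in an outcome |
| Pulse − Spread, untrained leg | a_P − a_S | Yes, as change in an outcome |
| Trained − untrained, over both diets | average of r_P and r_S | MPS only |
| Pulse − Spread of (trained − untrained) | r_P − r_S | No |

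Objective (iii) asks about r_P − r_S. Only the last row isolates it.

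**2. Precision of the missing contrast.** The protocol gives the group size (10 to 12) but no alpha, power, effect size, SD or between-leg correlation, so there is no power figure to reproduce. Section 13.2.5 says the size was chosen for time and cost. The group sizes agree with the stated total: 2 × 10 = 20 and 2 × 12 = 24.

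Assumptions: two-sided 5%, 80% power, equal SD in the two legs, effects in units of the per-leg SD, and between-leg correlation ρ from 0.3 to 0.9.

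- SD of the leg difference = √(2(1 − ρ)). This is 1.183, 1.000, 0.775 and 0.447 at ρ = 0.3, 0.5, 0.7 and 0.9.
- The detectable effect for a two-sample t-test in one leg, from the noncentral t with 2n − 2 degrees of freedom and noncentrality d√(n/2), is 1.325 SD for n = 10 and 1.197 SD for n = 12. As a check, the normal approximation √(2/n) × (1.960 + 0.842) gives 1.253 and 1.144, slightly smaller as expected.
- Detectable difference in the leg difference = single-leg figure × √(2(1 − ρ)):

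| ρ | n = 10 per group | n = 12 per group |
|---|---|---|
| 0.3 | 1.57 | 1.42 |
| 0.5 | 1.33 | 1.20 |
| 0.7 | 1.03 | 0.93 |
| 0.9 | 0.59 | 0.54 |

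The contrast is as sensitive as a single-leg test at ρ = 0.5, more sensitive above that and less sensitive below it.

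**3. Expected confidence interval at ρ = 0.5.** The half-width is t × √(2/n). For n = 10 it is 2.101 × 0.447 = 0.94 SD, and for n = 12 it is 2.074 × 0.408 = 0.85 SD.

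**4. Can the two single-leg tests stand in for it?** Simulations (40,000 runs per setting, 10 per group, ρ from 0.9 to 0.3) gave both legs the same diet effect. One leg's test was significant and the other's was not in 10% to 26% of trials at a 0.5 SD effect, and in 15% to 41% at 1.0 SD. The direct test on the leg difference rejected in about 5% throughout. Two per-leg results side by side therefore do not replace the contrast. These rates depend on the assumed effect and correlation, and the protocol does not say that it would draw conclusions in this way.

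**The case against.** The strongest objection is that objective (iii) is already addressed. Strength change in each leg is an outcome, Pulse versus Spread is planned for all outcomes, and both arms receive the same RET, so the randomised comparison of trained-leg change bears on the question. That is right in part. It answers whether diet alters strength gain in a trained leg, but not whether the alteration depends on training (step 1).

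A second objection is that modelling detail belongs in a statistical analysis plan that is not at hand. However, Section 13.2 itself fixes the comparisons and restricts the leg comparison to MPS, so the mismatch with Section 2.1 is stated in the protocol.

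A third is that the trial is exploratory and unpowered, so another contrast would settle little. It would indeed give a wide interval. But Section 13.2.5 intends these data to inform later sample sizes, and an estimate with its interval serves that purpose.

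A reader might also infer several stronger points that the documents do not support:

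- *The principal objective is unanswered.* Its wording can be read as two diet effects, one per leg, which Pulse versus Spread comparisons in each leg would answer.
- *Trained-leg change is spoiled by test learning.* Baseline strength comes from the pre-trial visit (Section 8.2: "unilateral knee extension exercise familiarisation (including 1-RM tests"), 14 to 28 days before day 0, so change to day 14 spans 28 to 42 days. This applies to both randomised arms and cancels in expectation when diets are compared.
- *The leg comparison ignores pairing.* Section 13.2 does not say that this t-test is unpaired.
- *T-tests are the wrong tool.* A two-sample t-test on the leg difference is sufficient. What is missing is the contrast.

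**Conclusion.** The point holds in a limited form. Objective (iii) asks a diet-by-RET question, the design and measurements can answer it, and Section 13.2 plans no contrast that isolates it. The planned comparison of trained-leg change answers it only in part. For MPS the same contrast would be useful, but the principal objective does not clearly require it.

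The gap itself follows from the text and needs no assumed figure. The precision does rest on assumptions: at ρ = 0.5, two-sided 5% and 80% power, the contrast detects 1.33 SD with 10 per group and 1.20 SD with 12. Over ρ from 0.3 to 0.9 the range is 1.57 down to 0.54 SD. It can therefore give an estimate and an interval, but not a firm conclusion unless the effect is large or the legs are highly correlated. This is a recommended and inexpensive correction, and it does not threaten the trial's validity.

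**What to change.** Add to Section 13.2 that, for 1-RM strength (change from baseline) and also for MPS, each participant's trained-minus-untrained difference will be compared between Pulse and Spread by a two-sample t-test. Equivalently, fit a mixed model with diet, leg and diet × leg as fixed effects and participant as a random effect. Report the contrast with a 95% confidence interval, alongside the Pulse versus Spread effect in each leg, and name it as the analysis for objective (iii).

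The cost is a change of wording, because both legs are already measured. There are two downsides. The variance of the leg difference is 2(1 − ρ) times that of a single leg, so it is noisier than trained-leg change when the two legs' changes correlate below 0.5. And if some of the strength gain carries over to the untrained leg, the difference understates the RET effect and is conservative. Reporting both the leg difference and the per-leg effects covers each case.
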